2.2 Secondary Objective

2.2.2 **In a pragmatic trial, estimate the effect of mPATH-CRC on completion of CRC screening within 16 weeks of visit.** We will query the electronic health record (EHR) at each study clinic to identify individuals aged 50 – 74 with no evidence of current CRC screening at the time of their clinic visit. We will then examine in the EHR whether these individuals complete CRC screening within 16 weeks of their index visit. The primary effectiveness analysis will compare the proportion of patients who complete screening between the pre- and post-implementation period in the “high touch” vs. “low touch” clinics. A secondary analysis will explore whether there is a dose-response relationship between use of mPATH-CRC and screening rates across all clinics.

2.2.3 **Determine the factors that facilitate or impede the maintenance of mHealth interventions like mPATH-CRC.** We will assess all clinics 12 months after implementation to identify those with high, low, and variable levels of maintenance. Using mixed methods that incorporate in-depth interviews with clinic staff, providers, and administrators, we will identify theory-based and organizational factors associated with sustained use of technology-based

EFFECTIVENESS AND IMPLEMENTATION OF MPATH-CRC: A MOBILE HEALTH SYSTEM FOR

COLORECTAL CANCER SCREENING

Wake Forest Baptist Comprehensive Cancer Center (WFBCCC)

WFBCCC # TBD

interventions like mPATH-CRC. These results will provide critical information to guide future large-scale dissemination and implementation trials.

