4.4.4. Study Cohort

mPATH is designed to be given to all English or Spanish-speaking patients on clinic check-in. Therefore, our implementation outcomes cohort will include all adult (18 and over) English or Spanish-speaking patients who are seen in the study clinics in the 12 months following the initial clinic mPATH launch date. Our effectiveness outcome will include all English or Spanish speaking patients aged 50-74 who are eligible for CRC screening based on EHR records in the 12 months prior to and 12 months following the initial clinic mPATH launch date. We can capture all data needed for this cohort because all the clinics have searchable electronic health records.

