4.4.5. Implementation and Clinic Randomization

We will randomly implement mPATH-CRC in 2 clinics (1 “high touch” and 1 “low touch”) until all 22 clinics are enrolled. To control for major organizational differences that could impact implementation, we will first select 2 clinics of similar size, then randomly assign one to receive the “high touch” strategy and the other the “low touch” strategy.

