4.5 Pragmatic Trial

To determine mPATH-CRC’s effectiveness, we will nest a pragmatic trial within the implementation study. We will query the electronic health record (EHR) at each study clinic to identify unscreened individuals aged 50 – 74 who completed a clinic visit with a physician or advanced practice professional 4 to 12 months prior to the implementation launch date, and 0 to 8 months after the implementation kick-off launch date. Specific inclusion criteria are detailed in Section 3.0. We will then examine in the EHR whether these individuals complete CRC screening within 16 weeks of their index visit.

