5.0 Outcome Measures

5.1 Definition of Time Points

The Implementation Date will be defined as the date of the clinic launch at each site. A “month” is defined as a 4 week time period. “Week 1” commences the day of clinic launch.

EFFECTIVENESS AND IMPLEMENTATION OF MPATH-CRC: A MOBILE HEALTH SYSTEM FOR

COLORECTAL CANCER SCREENING

Wake Forest Baptist Comprehensive Cancer Center (WFBCCC)

WFBCCC # TBD

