5.2 Primary Outcome

mPATH-CRC Reach: Proportion of all Spanish or English-speaking patients, ages 50 – 74, who are eligible for CRC screening and complete the mPATH-CRC program in the 6th month (weeks 21 – 24) following the implementation date. Patients who use mPATH™-CheckIn and are told they are due for CRC screening but advised to discuss screening with their doctor due to detected risk factors are also counted as having used mPATH™-CRC.

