- 5.3.10 mPATH™-CRC Maintenance: The proportion of patients aged 18 or older who complete mPATH™-CheckIn in months 7-12

EFFECTIVENESS AND IMPLEMENTATION OF MPATH-CRC: A MOBILE HEALTH SYSTEM FOR

COLORECTAL CANCER SCREENING

Wake Forest Baptist Comprehensive Cancer Center (WFBCCC)

WFBCCC # TBD

- 5.3.11 mPATH™-CRC Effectiveness: The proportion of patients aged 50-74 who are eligible for CRC screening who complete CRC screening within 16 weeks of their index visit to the clinic. Effectiveness is determined by comparing the proportion who complete screening in a pre-implementation cohort (months 12 - 4 before implementation) to a post-implementation cohort (months 1 - 8 after implementation).
- 5.3.12 CRC screening tests ordered: The outcome is defined as the proportion of patients aged 50-74 who are eligible for CRC screening who have a CRC screening test ordered (colonoscopy, flexible sigmoidoscopy, fecal testing for blood, or fecal DNA testing) within 16 weeks of their index visit to the clinic. This outcome will also be compared between the pre- and post-implementation cohorts.
- 5.3.13 Facilitators and barriers to maintenance (sustained use of mPATH™-CRC over time): These will be identified through semi-structured interviews. Interviews will explore how mPATH™-CRC was incorporated in the clinic's work flow and factors that affected maintenance such as intervention adaptations, organizational characteristics, and the champion's role. Interviews will be conducted with four members of each selected clinic: the clinic champion, one clinician, one front desk team member, and one medical assistant/nursing team member.

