 - Report that conflicts turn into fights

Analytic plan

Our primary analysis will compare the proportion of patients seen in the “pre” time period to the “post” time period who screen positive for either depression, fall risk, or safety at home. If a patient is seen more than once in a given time period, only the patient’s first visit in that time period will be included in the analyses. We will estimate the proportion who screen positive for each time period and report along with 95% confidence intervals. A chi-square test will be used to provide an unadjusted comparison between the “pre” and “post” proportions. Logistic regression models will then be used to compare the “pre” and “post” proportions while controlling for clinic and patient demographic variables. We will use the same analytic methods for our secondary outcomes. We will also conduct a sensitivity analysis for our primary outcome where we consider all patients’ visits during a given time period (and not limit analyses to a patient’s first visit in the time period only). For this sensitivity analysis, we will compare the proportion of patients who meet our primary outcome definition at any visit during the “pre” and “post” time periods.

Analytic adjustments due to COVID19 pandemic: Due to the COVID19 pandemic, all practices stopped using mPATH in March 2020, which is prior to the closure of the 60-day “post” time period for clinics #5 and #6 in our sample. Therefore, we will truncate the “post” time period for these two clinics to 30 days. To determine if this truncated time period affected our overall results, we will conduct the following sensitivity analyses: (1) limiting the analyses to only the first 4 clinics to enroll, and (2) limiting data collection to 30-days post- for all 6 clinics.

EFFECTIVENESS AND IMPLEMENTATION OF MPATH-CRC: A MOBILE HEALTH SYSTEM FOR
COLORECTAL CANCER SCREENING
Wake Forest Baptist Comprehensive Cancer Center (WFBCCC)
WFBCCC # TBD

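### After the March 2020 stop in mPATH use, the main Reach, Maintenance and effectiveness analyses have no suspension rule, and their mixed models omit randomisation pair and calendar period

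*Combined protocol and SAP*

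**What the plan says.** Appendix D states that "all practices stopped using mPATH in March 2020, which is prior to the closure of the 60-day" post window for clinics #5 and #6. It shortens that window to 30 days for those two clinics and adds two sensitivity analyses. All of this concerns the depression, falls and safety sub-study. Elsewhere the pandemic appears only as questions in the Appendix C interview guides.

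The main trial's clock is unchanged:
- Section 5.1: "The Implementation Date will be defined as the date of the clinic launch at each site", and a month is four weeks.
- Section 4.4.4: the implementation cohort is patients "who are seen in the study clinics in the 12 months following the initial clinic mPATH launch date".
- Section 5.2: the primary outcome counts eligible patients who "complete the mPATH-CRC program in the 6th month", weeks 21–24.
- Section 4.5: index visits for effectiveness fall "4 to 12 months prior to the implementation launch date, and 0 to 8 months after the implementation kick-off launch date".
- Section 5.3.11: the effectiveness outcome is the proportion of patients who "complete CRC screening within 16 weeks of their index visit to the clinic".

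On randomisation, Section 4.4.5 says "we will first select 2 clinics of similar size, then randomly assign one to receive the" high-touch strategy and the other the low-touch one. The mixed models in Sections 6.2 and 6.3 contain strategy or pre/post cohort, a random site effect and clinic size. They have no term for the pair and none for calendar period. Section 6.3 also plans an interrupted time series for screening, with a prior trend estimated within each clinic. Section 2.2 says "The primary effectiveness analysis will compare the proportion of patients who complete screening between the pre- and post-implementation period in the" high-touch versus the low-touch clinics.

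**The concern.** The text was revised after the stop, yet only a sub-study was adapted to it. Read as written, any suspended week inside a clinic's weeks 21–24 counts as failure to reach patients, and any suspended week in months 1–8 counts as post-implementation exposure.

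For Reach, a stop that hits both clinics of a pair pulls both arms down together. The difference shrinks a little. Because the model does not know which clinics were matched, the shared drop also enters as between-clinic variance. The stake is a missed benefit of the high-touch strategy.

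For the overall pre/post comparison the stake is bias. That model sets earlier visits against later ones without a calendar term, so a pandemic change in screening is credited to, or charged against, mPATH. The direction is not fixed, because clinics launched in the year after March 2020 could carry the pandemic in their pre cohort.

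**Working it through.** **The plan's own figure.** Table 3 gives 22 clinics for a difference of 0.15, ICC 0.03 and 80% power, with 30 patients per clinic, CV 25% and average use of 50%. Two-sided 5% is assumed here, since the level is not stated.
- Design effect: 1 + ((1 + 0.25²) × 30 − 1) × 0.03 = 1.926.
- Patients per arm before clustering: (1.960 + 0.842)² × (0.425 × 0.575 × 2) / 0.15² = 170.5.
- Clinics in total: 2 × 170.5 × 1.926 / 30 = 21.9, so 22.

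The sample size reproduces and is not in dispute.

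**Timing for clinics #5 and #6.** Launch is day 0. The Appendix D post window is days 14–73, and the stop came before it closed, so by day 73 at the latest.
- Weeks 21–24 are days 140–167, and 140 − 73 = 67 days after the stop at least.
- Eight months are 8 × 28 = 224 days, and (224 − 73)/224 = 67% of them follow the stop at least.
- If the 30-day truncation means use through about day 43, these become 140 − 44 = 96 days and (224 − 44)/224 = 80%.
- Follow-up is 16 × 7 = 112 days. A day-0 visit is followed to day 112, at least 112 − 73 = 39 days past the stop. Later visits run further past it.
- The pre cohort closes 4 × 28 = 112 days before launch, so its follow-up ends at launch and never reaches the stop.

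**Reach.** If one of 11 pairs had zero use in weeks 21–24, the expected difference is 0.15 × 10/11 = 0.136. The between-clinic variance becomes (10/11) × 0.03 × 0.25 + (1/11)(10/11) × 0.5² = 0.0275, against 0.4545 × 0.5455 = 0.248 in total. The implied ICC is therefore 0.11 instead of 0.03.

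Simulated power uses beta-binomial clinics, 11 pairs, 57.5% versus 42.5%, ICC 0.03 and two-sided clinic-level t-tests with 20 df unpaired or 10 df paired:

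| Use in the affected clinics | Unpaired | Paired |
|---|---|---|
| No disruption | 75% | 71% |
| One pair at 75% of normal | 71% | 70% |
| One pair at half | 61% | 68% |
| One pair at zero (worst case) | 25% | 66% |
| Two clinics at half, opposite arms, not a pair | 61% | 55% |

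The undisrupted 75% lies below the planned 80% because a t-test on clinic means replaces the normal approximation. With no true difference, the unpaired test rejects 5.1% of the time undisrupted, 2.2% with one pair at half use and 0.1% at zero use. The paired test stays near 5%.

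**Overall pre/post effectiveness.** With equal visits per clinic, clinics #5 and #6 are 2/22 = 9.1% of the post cohort. If the pandemic moved their completion by an assumed 10 points, the overall estimate moves 10 × 2/22 = 0.91 points. Each further fully affected clinic adds 10 × 1/22 = 0.45. The smallest detectable difference in Table 4 is 8.7 points.

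**The case against.** Counting from launch is defensible. Reach is an implementation outcome, and Sections 4.4.6 and 4.6 already expect some clinics to stop using mPATH and still survey and interview their staff. That stands, and the launch-date analysis should stay.

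The restart date is not given. Appendix C asks whether the practice still uses mPATH and has a branch for yes, so use may have resumed before weeks 21–24. A reader might infer that primary Reach was necessarily zero in the affected clinics. The documents do not support that, and the zero-use row is only a bound.

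A reader might also infer that the stop could produce a spurious advantage for one arm. When both clinics of a pair are affected, it does not: the unpaired test becomes conservative. That clinics #5 and #6 form a pair, and that paired clinics launch together, are both inferred. If the two are not a pair, pairing loses power.

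Finally, the plan does model time in one place. The Section 6.3 interrupted time series adjusts for each clinic's prior trend. It has no step at March 2020 and does not cover Reach, so it answers the concern only in part.

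**Conclusion.** The point holds as a missing rule plus two omitted model terms, and should be settled before outcomes are compared by arm. Clinics #5 and #6 have their whole primary window, all of Maintenance (months 7–12) and at least two-thirds of their effectiveness window after the stop. How many other clinics were affected is unknown.

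For Reach the harm is lost power, conditional on use not having recovered by weeks 21–24. It ranges from slight at 75% of normal use to severe at zero use, under the Table 3 assumptions and one affected pair. For overall pre/post effectiveness the harm is confounding of undetermined sign: about 0.9 points from these two clinics under an assumed 10-point shift, and more if others were affected.

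It would go too far to say that the between-strategy screening contrast, which Section 2.2 names as the primary effectiveness analysis, is confounded to the same degree. Both arms can share the shock, so it is less affected.

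**What to change.** 1. Record the stop and restart dates. Keep the analysis by original launch date over all clinics. Add a sensitivity analysis, fixed before outcomes are compared by arm and based on dates alone, that leaves out whole randomisation pairs whose weeks 21–24 overlap documented suspension. This costs the main analysis nothing.
2. Analyse strategy by randomisation pair in Section 6.2 and in the between-strategy comparisons of Section 6.3, with degrees of freedom based on the 11 pairs, at least as a pre-specified sensitivity analysis. If pairs share nothing, the price is about 4–5 points of power (75–76% to 71% in the clinic-level test).
3. In the overall pre/post model and the time series, add calendar-period terms, including a March 2020 step, defined on the 16-week follow-up window. Section 8.0 stores dates relative to day 0, so the honest broker must link launch dates. If the spread of launches does not allow these terms, report that estimate as confounded by the pandemic.

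Suspension-period visits should not be dropped from the main pre/post analysis. That could remove some clinics' post visits while keeping other clinics' pre visits from the same weeks, and it would not remove pandemic effects on completion.

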Appendix E – Data Transfer from non-Wake Forest Health Network Clinics

The following was the original plan for

In Wake Forest Health Network clinics, mPATH connects to the electronic health record (EHR) to import basic patient demographic data (e.g., patient name, medical record number, age) and prior colorectal cancer screening history information to determine if screening is needed. For clinics outside of the Wake Forest Health Network, this data will be imported to mPATH using secure file transfers. Non-WFHN clinics will upload a weekly flat file using Secure File Transfer Protocol to an encrypted, HIPAA-compliant Cloud-based server. The mPATH program will process the file, encrypt needed data elements, and then delete the original data file to protect data security. Additional data safeguards are outlined in Section 8.0. Formal data use agreements will be executed with all participating external sites. The flat file will include the following elements for patients who have upcoming scheduled appointments in the clinic(s):

- Patient medical record number
- Patient first name
- Patient middle name
- Patient last name
- Patient date of birth
- Date of last resulted FIT in chart
- Date of last resulted Colonoscopy in chart
